7.2.4.2 Withdrawal from Study

Patients will be informed that they have the right to withdraw from the study at any time, without prejudice to their medical care, and that they are not obliged to state their reasons.

Any withdrawal, and reasons for withdrawal, must be fully documented in the eCRF and source documents and the patient followed by the investigator/investigative staff.

Withdrawn patients may be replaced, as needed, to ensure 6 patients are enrolled into the 12-week Treatment Period of each treatment arm.

Patients will be withdrawn in the following circumstances:

- A patient's desire for withdrawal for any reason.
- Lost to follow-up (every effort must be made to contact the patient; a certified letter must be sent).
- An AE which, in the opinion of the investigator (or designee), necessitates withdrawal.
- Death.
- A patient's substantial non-compliance (Patient Diary and study drug compliance) or protocol violation.
- An investigator's (or designee's) opinion that continuing the patient in the study is not appropriate. The investigator (or designee) may withdraw a patient at any time if it is considered to be in the patient's best interest.
- Liver transplantation.
- Pregnancy

The reason and the date the patient is withdrawn from the study will be documented in the eCRF and source documents. If a patient is withdrawn from the study, the investigator/investigative staff will attempt to complete all End-of-Study (Visit 8) procedures within 14 days following premature withdrawal (i.e. 14 days following the final dose of the study drug).

7.2.4.3 Stopping Rules

The study will be halted if any of the following criteria are met:

- ≥ 2 patients experience a severe, nonserious AE that is considered to be related to study drug.
- ≥ 1 patient experiences a serious AE that is considered to be related to study drug.

If, following a SRC review, the sponsor deems it appropriate to restart the study, this can be done following approval of a substantial protocol amendment.

7.2.5 Study Termination by Sponsor

This study may be terminated at any time by Albireo, if significant safety concerns develop or, in the sponsor's judgment, there are no further benefits to be achieved from continuation of the study. In this event, Albireo/designee will inform the study investigators (or designees), institutions, and all regulatory authorities.

Albireo may temporarily or permanently discontinue the study at an investigative site at any time for safety, ethical, compliance, or other reasons. If this is necessary, Albireo will endeavor to provide advance notification to the site. If a site or the study is suspended or discontinued, the investigator/investigative staff will be responsible for promptly informing the Independent Ethics Committee (IEC)/Institutional Review Board (IRB) that this has happened. If required by local regulations, Albireo /designee will be responsible for informing the IEC/IRB and the Regulatory Authority of study or site discontinuation. In such an event, all study data and unused study drug must be returned to Albireo.

Events that could potentially trigger study discontinuation will undergo an expedited review by Albireo's internal Safety Review Team, which will reach an agreement prior to dosing new patients.

8 STUDY TREATMENT

8.1 Study Drug Supply and Storage

A3907 will be supplied in 10 mg tablets for oral administration. Tablets will be packaged and labelled in child-resistant containers with polypropylene caps.

Bottles of A3907 should be stored and dispensed in their original containers. All study drug must be stored according to the package label in a secure, limited-access location and may be dispensed only by the investigator (or designee) or by a member of the staff specifically authorised by the investigator (or designee). A3907 should be stored in a dry, clean, and well-ventilated area at 15°C to 25°C. Any deviations from the recommended storage conditions should be immediately reported to the sponsor and the study drug should not be used until approval by the sponsor.

Additional information on the study drug can be found in the provided study drug manual.

8.2 Study Drug Dose and Administration

Treatment with A3907 will be administered as a QD dose (single 10 mg tablet or three 10 mg tablets [30 mg]) or as a BID dose of three 10 mg tablets [30 mg] twelve hours apart on Day 0, followed by a 2-week dose confirmation period, before being administered at the same dose once daily for 12 weeks. Before each patient can begin the 12-week Treatment Period, individual PK evaluations will be conducted to ensure study drug exposure does not exceed that observed in the FIH study. If the exposures exceed the highest systemic exposure as described in [Section 5.4](#), the individual patient will be terminated early.

The dose for Arm 2 may be adjusted, after discussion at the SRC, based on review of PK data from patients in Arm 1, but it will not exceed 30 mg QD. The doses for Arms 3 and 4 may be adjusted, after discussion with the SRC, based on review of the PK data from patients in Arm 1 and 2, but will not exceed 30 mg BID.

Study drug will be dispensed to the patient at defined intervals from Visit 3 through Visit 7 ([Table 1](#)), together with instructions on how to store and take the drug. Study drug administration data, including whether each patient took each dose, will be documented through the Patient Diary and transferred to the study database at each visit.

Patients will be instructed to take the dose with food at approximately the same time each day in the morning. Patients should not crush or chew the tablet(s). Tablets should be

swallowed whole and should not be ingested if they are broken, cracked, or otherwise not intact. When swallowing the tablet intact, the patient should administer the dose with a glass of water. Dosing should not be repeated if a patient vomits after ingesting the daily dose. A QD dose missed by more than 12 hours should be skipped and the next prescribed dose should be taken at the usual time. If either of the BID doses are missed by > 6 hours, the dose should be skipped and the next prescribed dose should be taken at the usual time. If the patient is off A3907 for >5 half-lives of the study drug, the patient will be discontinued from the study.

On clinic visit days when laboratory assessments are conducted, study drug should be taken at the clinic after samples are collected. Patients will be required to fast for 4 hours prior to these study visits and breakfast will be provided at the time the study drug is administered. The first of the BID doses will be administered at the clinic and patients will be instructed to take the second of the BID doses at home, 12 hours after the first dose was received.

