
Methodology:
 
This is an open-label, Phase 2 study to evaluate the safety, tolerability, PK, and pharmacodynamic (PD) effects of 3 dose levels of A3907 (10 mg once daily [QD], 30 mg QD and 30mg twice daily [BID] administered orally for 12 weeks) in patients with PSC with and without a CRS.
 
The study includes up to a 2-week Screening Period, followed by administration of a single dose of A3907, followed by a 2-week period to confirm target exposure is reached before beginning a treatment period of 12 weeks, and an End of Study Visit 14 days after the last dose of study drug.
 
There will be a total of 8 scheduled visits during the study (including 1 Screening Visit).
 
The study will have four arms as follows:
 
 • Arm 1: patients with PSC dosed with 10mg QD • Arm 2: patients with PSC dosed with 30mg QD • Arm 3: patients with PSC dosed with 30mg BID • Arm 4: patients with PSC who have a CRS dosed with 30mg BID 
On Day 0, patients will receive a single daily dose of A3907 (10 mg QD [Arm 1], 30 mg QD [Arm 2], 30 mg BID [Arms 3 and 4]). Before each patient can begin the 12-week Treatment Period, individual PK evaluations will be conducted to ensure study drug exposure does not exceed the safety margin described in Section 5.4. If the exposures (C_{max} and AUC) exceed the highest systemic exposure as determined by the single ascending dose (SAD) data from the first in human (FIH) study, the individual patient will be terminated early.
 
Staggered Arms
 
Enrollment into treatment arms will be staggered as follows:
 
 • Arm 2 will begin after at least 3 patients in Arm 1 have completed 2 weeks of treatment and an internal Safety Review Committee (SRC) has reviewed safety and PK data; • Arms 3 and 4 will begin after at least 3 patients in Arm 2 have completed 2 weeks of treatment and the SRC has reviewed safety and PK data. Enrollment into Arm 4 will occur concurrently with Arm 3. 
Safety Review Committee (SRC)
		

Name of Sponsor/Company: Albireo AB	Name of Product: A3907	Name of Active Ingredient: A3907

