To mitigate risks related to potential variability in PK, patients will first receive a single daily dose of A3907 (10 mg once daily [QD] in Arm 1, 30 mg QD in Arm 2, or 30 mg twice daily [BID] in Arms 3 and 4). After review of each patient's PK data, if the systemic exposures do not exceed the highest systemic exposure previously established in the single dose part of Study A3907-001, CCI the dose will be confirmed, and the patient will begin administration of A3907 QD or BID for 12 weeks. If the exposures exceed the highest systemic exposure previously achieved in healthy subjects in the SAD part of Study A3907-001, individual patients will be terminated early.

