7 INVESTIGATIONAL PLAN

7.1 Overall Study Design and Plan

7.1.1 Description

This is an open-label, Phase 2 study to evaluate the safety, tolerability, PK, and PD effects of 3 dose levels of A3907, 10 mg (Arm 1), 30 mg (Arm 2) administered orally QD, or 30 mg BID in Arms 3 and 4 for 12 weeks in patients with PSC with and without a CRS (Figure 1). Eligible patients must have a clinical diagnosis of large-duct- PSC as evidenced by chronic cholestasis of more than 6 months duration. Patients must also have serum bile acids above the upper limit of normal (ULN) at the Screening Visit and ALP levels $> 1.5 \times \text{ULN}$ but $\leq 10 \times \text{ULN}$ repeated at least 2 weeks apart for baseline to reflect variability of $< 30\%$. If variability is $> 30\%$, a third ALP level may be obtained to determine the direction of abnormality or document stability. If stable ($< 30\%$ variance) the patient may be enrolled.

Prior to any other study procedures being conducted, the patient will have the nature of the study explained to him/her and be asked to sign an informed consent form (ICF). Informed consent must be obtained prior to any study procedures that do not form a part of the patient's normal care. After signing the ICF, patients will be evaluated for study eligibility. If not fasting at time of consent, patient will return to complete screening assessments after having fasted for 4 hours.

The study includes up to a 2-week Screening Period, followed by administration of a single dose of A3907, followed by a 2-week period to confirm the target exposure is reached before beginning a treatment period of 12 weeks. Each patient's PK will be reviewed and, if the systemic exposures do not exceed the highest systemic exposure previously established in the SAD portion of the FIH study CCI

CCI the dose will be confirmed and the patient will begin administration of A3907 daily for 12 weeks. If the exposures exceed the highest systemic exposure, the individual patient will be terminated early.

Enrollment into the treatment arms will be staggered with Arm 2 beginning after at least 3 patients in Arm 1 have completed 2 weeks of treatment and an internal Safety Review Committee (SRC) has reviewed safety and PK data. Enrollment into Arms 3 and 4 will occur

[figure not shown]
concurrently beginning after at least 3 patients in Arm 2 have completed 2 weeks of treatment and an internal SRC has reviewed safety and PK data.

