8.3.2 Blinding and Randomization of Study Drug

Blinding is not applicable as this is an open-label study. All patients will take A3907 administered orally once daily at approximately the same time each day as described in [Section 8.2](#). Patients will be assigned to treatment arms via an interactive voice/web response system (IXRS).

Patient Identification

After written informed consent is obtained from an eligible patient, an 8-digit patient identification number will be assigned. The first 2 digits will denote the country, followed by a 3-digit site number and a 3-digit patient sequence number. This number will be captured by the IXRS and integrated into the eCRF in Protocol A3907-002.

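### Protocol 8.2 and 8.3.2 prescribe once-daily dosing for the 12-week period with no exception for Arms 3 and 4, whose regimen is 30 mg BID

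*Protocol*

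**What the plan says.** The design sections agree with one another. The synopsis lists "Arm 3: patients with PSC dosed with 30mg BID" and gives Arm 4 the same regimen. Section 7.1.1 specifies "or 30 mg BID in Arms 3 and 4 for 12 weeks in patients with PSC". Section 5.4 says that once individual exposure has been reviewed, "the patient will begin administration of A3907 QD or BID for 12 weeks". SAP 3.1 and 3.3 repeat the BID regimen for Arms 3 and 4.

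The dosing sections differ. In 8.2, one sentence sets out the two QD regimens and the BID regimen for Day 0, then says the drug is held for two weeks "before being administered at the same dose once daily for 12 weeks". No arm is excepted. Later in 8.2: "Patients will be instructed to take the dose with food at approximately the same time each day in the morning". Section 8.3.2 states: "All patients will take A3907 administered orally once daily at approximately the same time each day", and refers back to 8.2.

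Section 8.2 also contains provisions that only make sense under BID dosing. It has a missed-dose rule, "If either of the BID doses are missed by > 6 hours, the dose should be skipped"; it caps the Arm 3 and 4 dose at 30 mg BID; and for clinic days it says "patients will be instructed to take the second of the BID doses at home, 12 hours after the first dose was received". Table 1 footnote e repeats the clinic-day rule.

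**The concern.** Section 8.2 is where a site looks to find out how the drug is taken. It contradicts both the design sections and itself on dosing frequency, and frequency is what defines the top dose level. Arms 2 and 3 take three 10 mg tablets per administration; they differ only in whether that happens once or twice a day.

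There is also a gap. The 12-hour interval is stated for Day 0 and for clinic days. For every other day of the 12 weeks, the only time-of-day instruction is for the morning, so the protocol text never says when the evening dose is taken at home.

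At stake are the delivered dose in Arms 3 and 4, the contrast between Arms 2 and 3, and the protocol-deviation record. Under 12.1 investigators may not depart from the protocol without an amendment, apart from narrow exceptions. As written, BID dosing departs from 8.2 and 8.3.2, and once-daily dosing departs from the synopsis, 5.4 and 7.1.1.

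**Working it through.** The plan gives no figure to reproduce, because no formal power calculation was done. The check is a comparison of texts followed by dose arithmetic.

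**Frequency for Arms 3 and 4 in the 12-week period**

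| Place | Frequency |
|---|---|
| Synopsis; protocol 7.1.1 | BID |
| Protocol 5.4 | BID for Arms 3 and 4 (QD or BID according to arm) |
| SAP 3.1, 3.3 | BID |
| Protocol 8.2: missed-dose rule, dose cap, clinic-day rule | BID |
| Protocol 8.2: main dosing sentence | Once daily |
| Protocol 8.2: time of day | One morning dose |
| Protocol 8.3.2 | Once daily, all patients |
| SAP 4.2 (counterpart of 8.3.2) | Daily; the word for once is absent |

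The three protocol statements in 8.2 and 8.3.2 with once-daily or morning-only wording are the outliers. The SAP's omission of that word fits leftover text in the protocol, but the documents do not show how the wording arose.

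**Inputs**

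- Tablet strength: 10 mg (protocol 8.1).
- Tablets per administration: 3 (protocol 8.2).
- Duration: 12 weeks = 12 × 7 = 84 days.
- Patients: 6 per arm, 4 arms (protocol 7.2.1).
- Compliance: 100 × tablets taken / (planned tablets per day × days) (SAP Appendix 3).

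**Dose in Arms 3 and 4**

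| | Intended (BID) | Literal 8.2 (once daily) |
|---|---|---|
| Tablets per day | 2 × 3 = 6 | 1 × 3 = 3 |
| Daily dose | 6 × 10 = 60 mg | 3 × 10 = 30 mg |
| Dosing occasions | 2 × 84 = 168 | 84 |
| Tablets over 84 days | 6 × 84 = 504 | 3 × 84 = 252 |
| Total dose | 5,040 mg | 2,520 mg |

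Patients covered: 6 + 6 = 12 of 24.

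**Compliance**

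- Takes three tablets a day, scored against six planned: 100 × 252 / 504 = 50%, in the SAP 7.3.2 category below 80%.
- Takes six tablets a day, scored against three planned: 100 × 504 / 252 = 200%, in the category above 120%.

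The SAP does not state planned tablets per day by arm, so the denominator depends on which protocol text the programmer follows.

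**Day count.** Day 14 to Day 98 with both end days counted is 98 − 14 + 1 = 85 days, which is how the SAP exposure rule would count it. The tablet totals become 6 × 85 = 510 and 3 × 85 = 255; the 2:1 ratio does not change.

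**Table 1 footnote h (side point).** For Arms 3 and 4 it times the 24-hour Day 0 sample relative to a dose the next morning. Table 1 next marks dosing at Visit 3, and 5.4 and 8.2 require individual PK review before the 12-week period starts. The footnote does not order a dose, but the phrase sits badly with that hold.

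**The case against.** The strongest reply is that this is editorial. The disputed sentence defines a BID dose and then refers to the same dose, so it is at odds with itself and is not a clear order to halve the dose. The rest of 8.2, Table 1 footnote e and every design section point to BID. Patients are assigned to arms through the IXRS, drug is dispensed with instructions, and a study drug manual and labels exist that may state the regimen correctly. Returned tablets are counted from Visit 4, two weeks into treatment, so a patient on half the dose should be noticed early. The full tablet totals assume that a misreading persists for 12 weeks and that the SRC has not lowered the Arm 3 and 4 dose, as 8.2 allows. The study period is 2022–2025 and the SAP cites a March 2025 drug dictionary, so dosing may be over.

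Most of this stands. The intent is recoverable, actual misdosing is not shown, the missing evening-dose instruction is established only for the protocol text, and footnote h is minor. None of it removes the contradiction. Unseen manuals and labels do not correct the protocol, and early detection through tablet counts depends on the site using six tablets a day as the expected number.

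**Conclusion.** The concern holds. Sections 8.2 and 8.3.2 prescribe once-daily dosing for all patients, which is wrong for Arms 3 and 4. If followed, the error halves the daily dose from 60 to 30 mg for up to 12 of 24 planned patients and makes the Arm 3 regimen identical to Arm 2. The totals assume 84 days, full adherence to the literal text and no SRC dose adjustment; the 2:1 ratio does not depend on the day count.

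This is an internal inconsistency to correct, not an open question about the regimen. Misreading it would under-dose, and it changes no endpoint, analysis set or sample size. It should be fixed because it sits in the operative dosing text and concerns the one feature that separates the regimens of Arms 2 and 3.

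**What to change.** - **Protocol 8.2 and 8.3.2:** replace the once-daily wording with *at the same dose and frequency (QD in Arms 1–2, BID about 12 hours apart in Arms 3–4) for 12 weeks*.
- **Protocol 8.2, time of day:** keep the morning instruction and add an evening dose about 12 hours later for Arms 3 and 4, on home days as well as clinic days.
- **Table 1 footnote h:** time the Arm 3 and 4 sample as *24 hours after the first Day 0 dose; after the second Day 0 dose no study drug is given until the individual PK review is complete*.
- **SAP 7.3.2 (optional):** state six planned tablets per day for Arms 3 and 4, subject to any SRC adjustment.

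The cost is a few lines of text and, if dosing continues, a short clarification to sites. If dosing has finished, put a clarification on file, check from diaries and tablet counts that Arms 3 and 4 took the drug twice daily, and confirm the compliance denominator. No new data are needed and the planned analyses do not change.

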In a first-in-human (FIH) study (Study A3907-001), A3907 or matching placebo were administered in capsules to healthy subjects as single oral doses of C to C mg or CCI oral doses of CCI mg for 7 days. Overall, A3907 was well tolerated when administered as single and multiple ascending doses (SAD/MAD) to the healthy subjects. There were no serious adverse events (SAEs), all treatment-emergent adverse events (TEAEs) were mild in

severity, and no subjects discontinued study drug or withdrew from the study due to TEAEs. The only treatment-related AEs that occurred in ≥ 2 subjects following single or multiple doses of A3907 were diarrhoea, abdominal pain, and headache. Pharmacokinetic analysis revealed that, with this formulation, A3907 was slowly absorbed (T_{\max} approximately [REDACTED] hours) and dose proportionality was demonstrated at single doses of [REDACTED]; the higher single dose of [REDACTED] mg did not result in increased exposure. No accumulation was seen following multiple [REDACTED] doses of [REDACTED] mg for 7 days, consistent with a half-life of approximately [REDACTED] hours. An increase in serum C4 concentrations and a decrease in serum LDL-C concentrations was observed at all A3907 doses; exploratory PK/pharmacodynamics (PD) results suggested a weak correlation between these PD parameters and A3907 PK parameters. While no clear trends were seen between A3907 concentrations and serum total bile acid concentrations, there was a decrease in total urine bile acids excreted at all treatment doses compared to placebo. Together, results of this study suggest that A3907 does inhibit ASBT but the net effect in the intended population is yet to be determined.

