9.3.6 Individual Patient Safety Monitoring

9.3.6.1 Liver Monitoring

Strategies to monitor markers of liver disease throughout the study are outlined below where the ULN will be based on central laboratory reference values. To make the distinction among the type of injury, and to make a causality assessment, the Roussel Uclaf Causality Assessment Method ([Appendix 2](#)) will be used.

For abnormalities classified as hepatic adverse events and/or hepatic decompensation, a PK sample should be collected as close to the onset of the event as possible.

If isolated transaminase elevations are observed, defined as:

Normal bilirubin AND absence of clinical hepatitis symptoms AND

- ALT or AST $\geq 5 \times$ ULN (if normal at baseline) OR
- ALT or AST $\geq 3 \times$ baseline (if abnormal at baseline) or > 500 U/L, whichever comes first

Then:

- a. Repeat liver profile (AST, ALT, bilirubin, and prothrombin time [PT] or INR) within 2 to 3 days
- b. Evaluate creatine phosphokinase (CPK) and lactate dehydrogenase (LDH)
- c. As needed (for example, persistent ALT/total bilirubin elevation or worsening of liver function), consider evaluation for alternative etiologies

Monitor the patient using the close observation guidelines found below.

If any ONE of the following criteria are met:

1. Transaminases (ALT or AST $\geq 3 \times$ baseline or 500 U/L, whichever comes first) AND bilirubin (total bilirubin $> 2 \times$ ULN) elevations
2. Transaminase elevations alone (ALT or AST $> 10 \times$ ULN or $5 \times$ baseline or absolute threshold of 800 U/L, whichever comes first) in presence of normal LDH and CPK
3. Total bilirubin increased, unrelated to hemolysis (elevated reticulocyte count) or established genetic diseases, such as Gilbert's syndrome

- a. Doubling if total bilirubin was < 3 mg/dL (equivalent to $51.3 \mu\text{mol/L}$) at baseline
OR
 - b. Increase by > 3 mg/dL (equivalent to $51.3 \mu\text{mol/L}$) if total bilirubin was ≥ 3 mg/dL (equivalent to $51.3 \mu\text{mol/L}$) at baseline
4. INR increase refractory to vitamin K administration
- a. Increase by > 1.5 if INR was normal at baseline OR
 - b. Increase by > 0.4 if INR was abnormal at baseline
5. Any increase in total bilirubin and transaminases if accompanied by EITHER a symptom of clinical hepatitis (e.g. vomiting, nausea, right upper quadrant pain) OR immunological reaction (rash or $> 5\%$ eosinophilia)

Then:

- a. Interrupt study medication

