- b. Initiate drug-induced liver injury work-up for alternative etiologies
- c. Repeat liver profile (AST, ALT, total bilirubin, direct bilirubin) and PT or INR within 48 to 72 hours
- d. Monitor the patient using the close observation guidelines found below.

Close Observation

For patients requiring closer observation:

- Repeat liver enzyme and serum bilirubin tests two or three times weekly.
Frequency of re-testing can decrease to once a week or less if abnormalities stabilise or the study drug has been discontinued and the patient is asymptomatic
- Obtain a more detailed history of symptoms and prior or concurrent diseases
- Obtain a history of concomitant drug use (including non-prescription medications and herbal and dietary supplement preparations), alcohol use, recreational drug use, and special diets
- Consider ruling out alternate etiology including acute viral hepatitis types A, B, C, D, and E; autoimmune or alcohol-associated liver disease; non-alcoholic steatohepatitis (NASH); hypoxic/ischemic hepatopathy; and biliary tract disease
- Obtain a history of exposure to environmental chemical agents
- Obtain additional tests to evaluate liver function, as appropriate (e.g. INR, direct bilirubin)
- If the Roussel Uclaf Causality Assessment Method (RUCAM) scoring meets DILI criteria, the patient must be discontinued from the study drug.

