9.3.6.2 De-challenge/Re-challenge for Liver and Clinical Hepatitis Monitoring

Re-challenge is not recommended if:

- If a patient has had possible/probable drug-induced liver injury according to RUCAM score.
- If a decompensation event has occurred (i.e. variceal haemorrhage, ascites, hepatic encephalopathy, etc.).

If an event is assessed as due to underlying cholestatic liver disease variability or another alternative aetiology is identified AND liver tests returned to baseline, re-challenge may be considered after consultation with the sponsor medical monitor.

If the ALT/total bilirubin elevations are observed after re-challenge, then repeat re-challenge is discouraged.

If a patient is permanently discontinued, monitoring should be continued as outlined in [Section 9.3.6.4](#).

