9.3.6.3 Diarrhoea

Study drug should be discontinued if a patient develops diarrhoea with at least 1 of the following concomitant signs or symptoms: grossly bloody stools, vomiting, dehydration requiring treatment with oral or intravenous rehydration and/or electrolyte imbalances, fever ($\geq 38^{\circ}\text{C}$) and/or the diarrhoea persists for 7 or more days.

If there is gross blood in stool, INR and platelets should be measured.

Study drug will be reintroduced when the symptoms have resolved. If the diarrhoea re-occurs within 1 week after the re-challenge with no alternate etiology, the patient will be permanently discontinued and monitored as outlined in [Section 9.3.6.4](#).

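### The rule removing any patient off drug for more than 5 half-lives conflicts with mandatory reintroduction after a diarrhoea stop, and the documents do not say which governs

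*Protocol*

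**What the plan says.** **Off-drug limit.** Protocol 8.2, at the end of the missed-dose instructions: "If the patient is off A3907 for >5 half-lives of the study drug, the patient will be discontinued from the study". No exception is attached and no other section is cited.

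**Diarrhoea.** Protocol 9.3.6.3 stops drug for diarrhoea with listed complications, or when "the diarrhoea persists for 7 or more days". It continues: "Study drug will be reintroduced when the symptoms have resolved". Permanent discontinuation follows only if diarrhoea returns within a week of re-challenge and has no other cause. No longest permitted gap is given.

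**Liver.** When any one of five criteria is met, Protocol 9.3.6.1 directs the site to "Interrupt study medication" and to "Repeat liver profile (AST, ALT, total bilirubin, direct bilirubin) and PT or INR within 48 to 72 hours". Under 9.3.6.2, if the event is put down to the underlying disease or another cause and tests are back to baseline, "re-challenge may be considered after consultation with the sponsor medical monitor". Again there is no limit on the gap.

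**Withdrawal sections.** Protocol 7.2.4.1 lists reasons to stop dosing while possibly remaining for safety monitoring. Section 7.2.4.2 lists reasons to leave the study. Neither mentions the 5-half-life rule.

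**Reporting.** Protocol 9.3 includes TEAEs leading to discontinuation in the primary safety analysis. SAP 9.1 has separate tables for TEAEs that led to interruption of treatment, to stopping treatment, and to leaving the study.

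**The concern.** Two mandatory instructions cover the same patient and point in opposite directions. Someone whose diarrhoea stop lasts longer than 5 half-lives leaves the study under 8.2 and goes back on drug under 9.3.6.3. Neither section refers to the other, and the withdrawal sections do not settle the matter, so the outcome depends on which page the site reads.

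This matters because safety and tolerability are the primary objective, and Protocol 5.5 names diarrhoea among the most common drug-related events in the first-in-human study. The choice of section determines:

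- whether the patient stays on drug and can contribute Week 12 data;
- whether the case appears in the SAP as an interruption or as a study discontinuation;
- whether follow-up continues on drug or ends early.

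The wording of 9.3.6.3 adds to the uncertainty: it says the drug should be discontinued for what it then treats as a temporary stop, whereas the liver section speaks of interruption.

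**Working it through.** The plan has no figure to reproduce here. The check compares the texts and then asks how readily the limit could be passed.

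**1. The rules side by side**

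| Section | Force | Condition | Longest gap allowed |
|---|---|---|---|
| 8.2 | mandatory | off drug | 5 half-lives, then study exit |
| 9.3.6.3 | mandatory | symptoms resolved | none stated |
| 9.3.6.2 | optional, with medical monitor | tests back to baseline, other cause | none stated |

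For a diarrhoea gap G and half-life t½, 8.2 and 9.3.6.3 are compatible if G ≤ 5 × t½ and contradictory if G > 5 × t½. This follows from the wording and needs no value of t½.

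**2. Where the limit falls**

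The half-life is redacted, but Protocol 5.2.3 gives it in hours. Assumed range: 4 to 24 h. Limit = 5 × t½.

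| Assumed t½ (h) | Limit (h) | Limit (days) | Accumulation ratio R |
|---|---|---|---|
| 4 | 20 | 0.83 | 1.02 |
| 8 | 40 | 1.67 | 1.14 |
| 12 | 60 | 2.5 | 1.33 |
| 24 | 120 | 5.0 | 2.0 |

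R = 1/(1 − 2^(−24/t½)), assuming once-daily dosing and one-compartment behaviour. Protocol 5.2.3 reports: "No accumulation was seen following multiple" doses over 7 days. That favours the upper rows of the table but does not fix a value.

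**3. Comparison with the gaps**

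- Diarrhoea: a stop lasting more than 20 to 120 h passes the limit, depending on t½. The 7-day trigger is time with diarrhoea before the stop, not time off drug. It shows that slow-resolving cases are in scope but does not measure the gap.
- Liver: the limit exceeds 48 h only if t½ > 48/5 = 9.6 h, and 72 h only if t½ > 72/5 = 14.4 h. Both thresholds lie inside the assumed range, so the retest alone may or may not pass the limit. Waiting for a return to baseline can only lengthen the gap.

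**4. Size in the tables**

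Protocol 7.2.1 plans 6 patients in each of 4 arms, 24 in all. One patient classified differently moves an arm's rate by 1/6 = 16.7 percentage points and the overall rate by 1/24 = 4.2 points.

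**5. Chance that the question arises**

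The documents give no frequency. Let p be the assumed share of patients with a safety stop that outlasts the limit. The chance of at least one among n patients is 1 − (1 − p)^n.

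| Assumed p | n = 6 | n = 24 |
|---|---|---|
| 5% | 27% | 71% |
| 10% | 47% | 92% |
| 30% | 88% | >99% |

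This illustrates the range; it is not a forecast.

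**The case against.** Several points on the other side stand.

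- **Context.** The 8.2 sentence closes a paragraph on missed doses, so a site could take it to mean missed doses only. That is a sensible reading, but the sentence speaks of being off drug, for any reason, and nothing confines it.
- **The liver path.** A reader might infer that 8.2 makes liver re-challenge unusable. The documents do not support that: re-challenge is optional and goes through the sponsor's medical monitor, so it can operate inside an 8.2 limit.
- **The length of the limit.** A reader might turn the absence of accumulation into a firm bound. Taking R as at most 1.1 to 1.3 under once-daily dosing gives t½ of at most 6.9 to 11.3 h and a limit of 35 to 57 h. That rests on a chosen threshold and a redacted half-life, from capsules in healthy subjects, whereas this study gives tablets to patients and Protocol 5.4 warns of PK variability. The result also overlaps the 48 to 72 h retest, so it does not prove a breach.
- **The scheduled gap.** A reader might infer that the two weeks after the Day 0 dose breach 8.2 for everyone. They do not: section 8.2 itself schedules that period, and 7.1.1 describes a single dose "followed by a 2-week period to confirm the target exposure is reached before beginning a treatment period of 12 weeks".
- **Effect on results.** Relabelling a case does not remove the TEAE. The SAP 9.1 tables are not stated to be mutually exclusive, and SAP 9.1 provides patient listings, so individual cases remain visible.
- **Frequency.** Protocol 5.2.3 reports only mild TEAEs and no discontinuation because of one in the first-in-human study, and 9.3.6.3 covers only complicated or prolonged diarrhoea.

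The documents also disagree on replacing patients who discontinue for an AE (Protocol 7.1.1 against SAP 4.1). That is a separate inconsistency.

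These points narrow the concern. None reconciles 8.2 with 9.3.6.3.

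**Conclusion.** The contradiction between 8.2 and 9.3.6.3 is in the current text and applies whenever a diarrhoea stop exceeds 5 half-lives. The liver section is a secondary case, because re-challenge there is only permitted.

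How often the conflict occurs cannot be determined from the documents. With an assumed half-life of 4 to 24 h the limit is 20 to 120 h, so a conflict is plausible, but a short interruption would cause none.

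The direct effect is on whether the patient stays on drug to Week 12 and on the split between interruption and study discontinuation, at 16.7 percentage points per patient in an arm of 6. A reader might infer that the primary endpoint is itself misclassified. It is not: TEAE incidence changes only indirectly, through time on drug and follow-up.

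The text should still be corrected, because two mandatory rules on patient handling collide and feed the discontinuation part of the primary safety analysis. Which clinical rule should stand is for the sponsor.

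**What to change.** 1. **Protocol.** Reconcile 8.2 with 9.3.6.3 and 9.3.6.2. State whether the 5-half-life rule applies to interruptions that the protocol directs for safety, and from what time the gap is counted. Carry the answer into 7.2.4, including whether the rule ends treatment only or study participation as well.
2. **SAP 9.1.** State how a safety stop is classified when drug is resumed, when it is not resumed, and when the off-drug limit is what ends participation. Say whether one event may appear in more than one of the three tables.
3. **SAP listing.** Flag each safety-related dosing gap with its length and outcome. The duration formula in SAP 7.3.1 runs from first to last dose and does not show gaps.

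The drafting is a sentence or two in the protocol and a short rule in the SAP. The protocol change is not purely administrative, so under Protocol 13.1 it needs ethics committee and, where applicable, authority approval. If dosing has already finished, the SAP items can still be settled before database lock.
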